10.4.1. Definition of AE and ADE

AE and ADE Definition

- An AE is defined in Appendix 2 ([Section 10.2.1](#)).
- An ADE is defined as an AE related to the use of an investigational medical device. This definition includes any AEs resulting from insufficient or inadequate instructions for use, deployment, implantation, installation, or operation, or any malfunction of the investigational medical device as well as any event resulting from use error or from intentional misuse of the investigational medical device.

10.4.2. Definition of SAE, SADE, and USADE

SAE Definition

- An SAE is defined in Appendix 2 ([Section 10.2.3](#)).

SADE Definition

- An SADE is defined as an adverse device effect that has resulted in any of the consequences characteristic of an SAE.
- Any device deficiency that might have led to an SAE if appropriate action had not been taken, intervention had not occurred, or circumstances had been less fortunate.

USADE Definition

- A USADE is a serious adverse device effect that by its nature, incidence, severity, or outcome has not been identified in the current version of the risk analysis management file.

10.4.3. Definition of Device Deficiency

Device Deficiency Definition

- A device deficiency is an inadequacy of a medical device with respect to its identity, quality, durability, reliability, safety, or performance. Device deficiencies include malfunctions, use errors, and inadequate information supplied by the manufacturer.

10.4.4. Recording/Reporting and Follow-Up of Medical Device Deficiencies

Device Deficiency Recording

- When a device deficiency occurs, it is the responsibility of the investigator to review all documentation (eg, hospital progress notes, laboratory reports, and diagnostic reports) related to the event.
- The investigator will then record all relevant device deficiency information in the participant's medical records, in accordance with the investigator's normal clinical practice and will also capture the required information on the Medical Device Complaint form.
- It is not acceptable for the investigator to send photocopies of the participant's medical records to Pfizer Safety in lieu of following the reporting process described in the Medical Device Complaint form.
- There may be instances when copies of medical records for certain cases are requested by Pfizer Safety. In this case, all participant identifiers, with the exception of the participant number, will be redacted on the copies of the medical records before submission to Pfizer Safety.
- If the investigator determines that the medical device deficiency may have injured the participant (ie, the medical device deficiency is associated with an AE or SAE), then the investigator will attempt to establish a diagnosis of the event based on signs, symptoms, and/or other clinical information. Whenever possible, the diagnosis will be documented in the participant's medical record and recorded as the AE or SAE rather than the individual signs/symptoms. Requirements for

recording and reporting an AE or SAE are provided in Appendix 2 ([Section 10.4.1](#)).

- For device deficiencies, it is very important that the investigator describes any corrective or remedial actions taken to prevent recurrence of the incident.
 - A remedial action is any action other than routine maintenance or servicing of a medical device where such action is necessary to prevent recurrence of a device deficiency. This includes any amendment to the device design to prevent recurrence.

Assessment of Causality Occurring in Conjunction With a Medical Device Deficiency

- If an AE or SAE has occurred in conjunction with a medical device deficiency, the investigator must assess the relationship between each occurrence of the AE or SAE and the medical device deficiency. The investigator will use clinical judgment to determine the relationship.
- A “reasonable possibility” of a relationship conveys that there are facts, evidence, and/or arguments to suggest a causal relationship, rather than a relationship cannot be ruled out.
- Alternative causes, such as underlying disease(s), concomitant therapy, and other risk factors, as well as the temporal relationship of the event to study intervention administration will be considered and investigated.
- The investigator will also consult the IB and/or product information, for marketed products, in his/her assessment.
- For each device deficiency, the investigator must document in the medical notes that he/she has reviewed the device deficiency and has provided an assessment of causality.
- There may be situations in which an SAE has occurred and the investigator has minimal information to include in the initial report to the sponsor. However, it is very important that the investigator always make an assessment of causality for every event before the initial transmission of the SAE data to the sponsor.
- The investigator may change his/her opinion of causality in light of follow-up information and send an SAE follow-up report with the updated causality assessment.
- The causality assessment is one of the criteria used when determining regulatory reporting requirements.

Follow-Up of Medical Device Deficiency

- The investigator is obligated to perform or arrange for the conduct of supplemental measurements and/or evaluations, as medically indicated or as requested by the sponsor to elucidate the nature and/or causality of the device deficiency as fully as possible. This may include additional laboratory tests or investigations, histopathological examinations, or consultation with other healthcare providers.
- New or updated information regarding the nature of the device deficiency will be recorded in the originally completed Medical Device Complaint form.
- New or updated information regarding any SAE that was potentially associated with the medical device deficiency will be submitted to Pfizer Safety on the Vaccine SAE Reporting Form within 24 hours of receipt of the information, according to the requirements provided in [Appendix 2](#).

10.4.5. Reporting of SAEs

Reporting of an SAE to Pfizer Safety must be performed according to the processes described in Appendix 2 ([Section 10.2.4](#)).

10.4.6. Reporting of SADEs

SADE Reporting to Pfizer Safety

Note: There are additional reporting obligations for medical device deficiencies that are potentially related to SAEs (ie, an SADE) that must fulfill the legal responsibility to notify appropriate regulatory authorities and other entities about certain safety information relating to medical devices being used in clinical studies.

- Any device deficiency that is associated with an SAE must be reported to the sponsor within 24 hours after the investigator determines that the event meets the definition of a device deficiency.
- The sponsor shall review all device deficiencies and determine and document in writing whether they could have led to an SAE. These shall be reported to the regulatory authorities and IRBs/ECs as required by national regulations.

10.5. Appendix 5: Alternative Measures During Public Emergencies

The alternative study measures described in this section are to be followed during public emergencies, including the COVID-19 pandemic. This appendix applies for the duration of the COVID-19 pandemic and will become effective for other public emergencies only upon written notification from Pfizer.

Use of these alternative study measures is expected to cease upon the return of business as usual (including the lifting of any quarantines and travel bans/advisories).

10.5.1. Telehealth Visits

In the event that in-clinic study visits cannot be conducted, every effort should be made to follow up on the safety of study participants at scheduled visits per the [SoA](#) or unscheduled visits. Telehealth visits may be used to continue to assess participant safety and collect data points. Telehealth includes the exchange of healthcare information and services via telecommunication technologies (eg, audio, video, video-conferencing software) remotely, allowing the participant and the investigator to communicate on aspects of clinical care, including medical advice, reminders, education, and safety monitoring. The following assessments must be performed during a telehealth visit.

- Review and record any AEs and SAEs since the last contact. Refer to [Section 8.3](#).
- Review and record any new or changes in concomitant medications to treat SAEs since the last contact.

Study participants' parent(s)/legal guardian(s) must be reminded to promptly notify site staff about any change in their health status.

10.5.2. Study Intervention

If the safety of a trial participant is at risk because they cannot complete required evaluations or adhere to critical mitigation steps, then discontinuing that participant from study intervention must be considered.

10.6. Appendix 6: Abbreviations

The following is a list of abbreviations that may be used in the protocol.

Abbreviation	Term
7vPnC	7-valent pneumococcal conjugate vaccine
13vPnC	13-valent pneumococcal conjugate vaccine
20vPnC	20-valent pneumococcal conjugate vaccine
ADE	adverse device effect
AE	adverse event
ALT	alanine aminotransferase
AOM	acute otitis media
AST	aspartate aminotransferase
CAP	community-acquired pneumonia
CBER	Center for Biologics Evaluation and Research (US)
CDC	Centers for Disease Control and Prevention (US)
CFR	Code of Federal Regulations
CHMP	Committee for Medicinal Products for Human Use
CI	confidence interval
CIOMS	Council for International Organizations of Medical Sciences
CK	creatinine kinase
CONSORT	Consolidated Standards of Reporting Trials
COVID-19	coronavirus disease 2019
CRF	case report form
CRM ₁₉₇	cross-reactive material 197
CRO	contract research organization
CSR	clinical study report
DILI	drug-induced liver injury
DMC	data monitoring committee
DU	dispensable unit
EC	ethics committee
ECC	emergency contact card
ECDC	European Centre for Disease Prevention and Control
ECG	electrocardiogram
EDB	exposure during breastfeeding
eCRF	electronic case report form
e-diary	electronic diary
CCI	
EDP	exposure during pregnancy
EMA	European Medicines Agency
EU	European Union
EudraCT	European Clinical Trials Database
FDA	Food and Drug Administration (US)

PFIZER CONFIDENTIAL

Abbreviation	Term
GCP	Good Clinical Practice
GGT	gamma-glutamyl transferase
CCI	
GMR	geometric mean ratio
GMT	geometric mean titer
HIV	human immunodeficiency virus
IB	investigator's brochure
ICD	informed consent document
ICH	International Council for Harmonisation
ID	identification
IgG	immunoglobulin G
IND	investigational new drug application
INR	international normalized ratio
IPAL	Investigational Product Accountability Log
IPD	invasive pneumococcal disease
IP manual	investigational product manual
IRB	institutional review board
IRT	interactive response technology
ISO	International Organization for Standardization
IWR	interactive Web-based response
LFT	liver function test
LLOQ	lower limit of quantitation
MDR	medical device regulation
MedDRA	Medical Dictionary for Regulatory Activities
OPA	opsonophagocytic activity
PI	principal investigator
CCI	
PPE	personal protective equipment
PPSV23	23-valent pneumococcal polysaccharide vaccine
PT	prothrombin time
QTL	quality tolerance limit
CCI	
SADE	serious adverse device effect
SAE	serious adverse event
SAP	statistical analysis plan
SARS-CoV-2	severe acute respiratory syndrome coronavirus 2
SmPC	summary of product characteristics
SoA	schedule of activities
SOP	standard operating procedure
SRM	study reference manual
SRSD	single reference safety document

Abbreviation	Term
SUSAR	suspected unexpected serious adverse reaction
TBili	total bilirubin
ULN	upper limit of normal
US	United States
USADE	unanticipated serious adverse device effect
VT	vaccine-type
WHO	World Health Organization

1. VERSION HISTORY

Table 1. Summary of Changes

Version/ Date	Associated Protocol Amendment	Rationale	Specific Changes
1 04 May 2022	Original 10 Dec 2021	N/A	N/A

[figure not shown]
2. INTRODUCTION

This SAP provides the detailed methodology for summary and statistical analyses of the data collected in Study B7471027. This document may modify the plans outlined in the protocol; however, any major modifications of the primary endpoint definition or its analysis will also be reflected in a protocol amendment.

2.2. Study Objectives, Endpoints, and Estimands

Objectives	Endpoints	Estimands
Primary Safety Objective	Primary Safety Endpoints	Primary Safety Estimands
To describe the safety profile of 20vPnC	 Prompted local reactions (redness, swelling, and pain at the injection site) Prompted systemic events (fever, decreased appetite, drowsiness/increased sleep, and irritability) AEs SAEs 	In participants receiving at least 1 dose of study intervention with safety follow-up after the assigned vaccination: • The percentage of participants reporting prompted local reactions within 7 days after the last assigned vaccination in each group • The percentage of participants reporting prompted systemic events within 7 days after the last assigned vaccination in each group • The percentage of participants reporting AEs within 1 month after the last assigned vaccination in each group • The percentage of participants reporting SAEs within 1 month after the last assigned vaccination in each group
Primary Immunogenicity Objective	Primary Immunogenicity Endpoint	Primary Immunogenicity Estimand
To describe the immune responses to the additional 7 serotypes after 1 or 2 doses of 20vPnC	Pneumococcal serotype-specific IgG concentration	In participants complying with the key protocol criteria (evaluable participants) in each group: • Percentages of participants with predefined serotype-specific IgG concentrations for the 7 additional serotypes 1 month after the last assigned vaccination
Secondary Immunogenicity Objective	Secondary Immunogenicity Endpoints	Secondary Immunogenicity Estimands
To further describe the immune response of 20vPnC after 1 or 2 doses	 Pneumococcal serotype-specific IgG concentration Pneumococcal serotype-specific OPA titers 	 In evaluable participants in each group: IgG GMCs for the vaccine serotypes 1 month after the last assigned vaccination Percentages of participants with predefined IgG concentrations for the 13 matched serotypes 1 month after the last assigned vaccination OPA GMTs for the vaccine serotypes 1 month after the last assigned vaccination

2.3. Study Design

This Phase 3, multicenter, randomized, partially double-blind study will be conducted at investigator sites in Europe.

Approximately 360 toddlers ≥12 to <24 months of age at the time of consent, who previously received 2 infant doses of 13vPnC (prior to 12 months of age), will be enrolled and randomized in a 1:1:1 ratio to receive either 1 or 2 doses of 20vPnC, or 1 dose of 13vPnC (control). The vaccine in toddlers randomized to receive 1 dose will be double-blind, as 20vPnC and 13vPnC have the same appearance and a single dose will be administered at Visit 1 of the study. Toddlers randomized to receive 1 dose are to return approximately 1 month later for Visit 2 for collection of safety information and a blood draw. For participants randomized to 2 doses of 20vPnC, the parent(s)/legal guardian(s) and site staff will know that these participants will need to return for a second vaccination visit and that they will receive 20vPnC at both Visit 1 and Visit 2 (approximately 2 months later), and after the second dose will return approximately 1 month later for Visit 3 for collection of safety information and a blood draw. The last assigned vaccinations will be the single vaccination at Visit 1 in the groups randomized to receive 1 dose of 20vPnC or 13vPnC (control) and the second vaccination given at Visit 2 in the group randomized to receive 2 doses.

Blood will be drawn from all participants for immunogenicity assessments before administration of the study intervention and 1 month after the vaccination (last vaccination in the group receiving 2 doses) in each vaccine group.

Participants will be observed for 30 minutes after each vaccination and any reactions occurring during that time will be recorded as immediate AEs. Prompted local reactions (redness, swelling, and pain at the 20vPnC or 13vPnC injection site), systemic events (fever, decreased appetite, drowsiness/increased sleep, and irritability), and use of antipyretic/pain medications occurring within 7 days after each vaccination will be collected via a provided

e-diary (or e-diary application). AEs and SAEs will be collected from the signing of informed consent to 1 month after the last dose.

3. ENDPOINTS AND BASELINE VARIABLES: DEFINITIONS AND CONVENTIONS

3.1. Primary Endpoints

3.1.1. Primary Safety Endpoints

- Prompted local reactions (redness, swelling, and pain at the injection site) within 7 days after the last assigned vaccination.
- Prompted systemic events (fever, decreased appetite, drowsiness/increased sleep, and irritability) within 7 days after the last assigned vaccination.
- AEs from vaccination to 1 month after the last assigned vaccination.
- SAEs from vaccination to 1 month after the last assigned vaccination.

3.1.1.1. Local Reactions

The local reactions assessed and reported in the e-diary are redness, swelling, and pain at the 20vPnC or 13vPnC injection site, from Day 1 through Day 7 after each dose, where Day 1 is the day of each dose. This section describes derivations with details for the assessment of local reactions: severity level, duration, and onset day.

Severity and Maximum Severity

Redness and swelling will be measured and recorded in measuring device (caliper) units (range: 1 to 14, and >14), and then categorized during analysis as mild, moderate, or severe based on the grading scale in Table 2. Grade 4 will not be collected in the e-diary but as an AE on the CRF. Measuring device units can be converted to centimeters according to the following scale: 1 measuring device unit = 0.5 cm. Pain at the vaccine injection site will be assessed by the participant's parent(s)/legal guardian(s) as mild, moderate, or severe according to the grading scale in Table 2.

Table 2. **Grading Scales for Local Reactions**

Local Reaction	GRADE 1	GRADE 2	GRADE 3a	GRADE 4b
	Mild	Moderate	Severe	
Redness	1 to 4 caliper units	5 to 14 caliper units	>14 caliper units	Necrosis or exfoliative
	(or measuring device	(or measuring device	(or measuring device	dermatitis
	units)	units)	units)	
	=	=	=	
	>0 to 2.0 cm	>2.0 to 7.0 cm	>7.0 cm	
Swelling	1 to 4 caliper units	5 to 14 caliper units	>14 caliper units	Necrosis
	(or measuring device	(or measuring device	(or measuring device	
	units)	units)	units)	
	=	=	=	
	>0 to 2.0 cm	>2.0 to 7.0 cm	>7.0 cm	
Pain at injection	Hurts if gently	Hurts if gently	Causes limitation of	Emergency room visit
site	touched	touched, with crying	limb movement	or hospitalization for
	(eg, whimpers,			severe pain
	winces, protests, or			(tenderness) at
	withdraws)			injection site

Note: If the size of the redness and/or swelling falls between 2 measuring device units, the higher measuring device unit number will be recorded in the e-diary.

- a. Parents/legal guardians of the participants experiencing local reactions >14 caliper units (>7.0 cm) are to be contacted by the study site. An unscheduled visit may be required.
- b. Grade 4 assessment should be made by the investigator. Grade 4 will not be collected in the e-diary but as an AE on the CRF.

For each local reaction after each dose, the maximum severity grade will be derived for the e-diary collection period (Day 1 through Day 7, where Day 1 is the day of each dose) as follows:

maximum severity grade = highest grade (maximum severity) within 7 days after the last assigned vaccination (Day 1 through Day 7) among severity grades reported for that local reaction in the e-diary.

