8.2.3.1. Local Reactions

For the first 7 days following each study vaccination (Day 1 through Day 7, where Day 1 is the day of vaccination), the participant's parent(s)/legal guardian(s) will be asked to assess redness, swelling, and pain at the 20vPnC or 13vPnC injection site and to record the symptoms in the e-diary in the evening. Redness and swelling will be measured and recorded in measuring device (caliper) units (range: 1 to >14; an entry in the e-diary of 15 will denote >14), and then categorized during analysis as mild, moderate, or severe based on the grading scale in Table 1. Measuring device units can be converted to centimeters according to the following scale: 1 measuring device unit = 0.5 cm. Pain at the vaccine injection site will be assessed by the participant's parent(s)/legal guardian(s) as mild, moderate, or severe according to the grading scale in Table 1. The participant's parent(s)/legal guardian(s) will be prompted to contact the investigator if the participant experiences a severe (Grade 3) or above local reaction to assess the reaction and perform an unscheduled assessment or visit as appropriate.

Only an investigator is able to classify a participant's local reaction as Grade 4, after physical examination of the participant or documentation from another medically qualified source (eg, emergency room or hospital record). If a participant experiences a Grade 4 local reaction, the investigator must immediately notify the sponsor. Site staff will educate the participant's parent(s)/legal guardian(s) regarding signs and symptoms that would prompt site contact.

The procedure for notification of the sponsor is provided in the SRM or equivalent.

Table 1. Grading Scales for Local Reactions

Local Reaction	GRADE 1 Mild	GRADE 2 Moderate	GRADE 3 ^a Severe	GRADE 4 ^b
Redness	1 to 4 caliper units (or measuring device units) = >0 to 2.0 cm	5 to 14 caliper units (or measuring device units) = >2.0 to 7.0 cm	>14 caliper units (or measuring device units) = >7 cm	Necrosis or exfoliative dermatitis
Swelling	1 to 4 caliper units (or measuring device units) = >0 to 2.0 cm	5 to 14 caliper units (or measuring device units) = >2.0 to 7.0 cm	>14 caliper units (or measuring device units) = >7 cm	Necrosis

Table 1. Grading Scales for Local Reactions

Local Reaction	GRADE 1 Mild	GRADE 2 Moderate	GRADE 3 ^a Severe	GRADE 4 ^b

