9.3.4. Primary Endpoint(s)/Estimand(s) Analysis

Objective	Estimands	Statistical Analysis Methods
Safety	
 Proportions of participants with local reactions (redness, swelling, and pain at the injection site) within 7 days after the last assigned vaccination from each group Proportions of participants with systemic events (fever, decreased appetite, irritability, and drowsiness/increased sleep) within 7 days after the last assigned vaccination from each group 	
 Descriptive summary statistics for participants with each local reaction/systemic event within 7 days after each dose by maximum severity and cumulatively across severity levels
	
 AEs from vaccination to 1 month after the last assigned vaccination in each group 	
 Three-tier approach
	
 SAEs from vaccination to 1 month after the last assigned vaccination in each group 	
 Descriptive summary statistics

Objective	Estimands	Statistical Analysis Methods
Immunogenicity	
 Percentage of participants with IgG concentrations to the 7 additional serotypes with a predefined level^a 1 month after the last assigned vaccination in each group 	
 Descriptive summary statistics •

a. The predefined level is 0.35 µg/mL for all 7 additional serotypes.

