3.1.1.2. Systemic Events (Systemic Event Symptoms and Fever)

The systemic events assessed and recorded in the e-diary are fever, decreased appetite, drowsiness/increased sleep, and irritability from Day 1 through Day 7, where Day 1 is the day of each dose. The derivations for systemic events will be handled similarly to the way local reactions are handled for severity level, duration, and onset day (see Section 3.1.1.1).

The systemic events of decreased appetite, irritability, and drowsiness/increased sleep will be assessed by participant's parent(s)/legal guardian(s) as mild, moderate, or severe according to the grading scale in Table 3. Grade 4 will not be collected in the e-diary but will be collected as an AE on the CRF.

Table 3. Grading Scales for Systemic Events

Systemic Event	Mild	Moderate	Severe	
	Grade 1	Grade 2	Grade 3	Grade 4 ^a
Decreased appetite	Decreased	Decreased oral	Refusal to feed	Emergency room visit or
(loss of appetite)	interest in eating	intake		hospitalization for severe
				decreased appetite (loss of
				appetite)
Drowsiness	Increased or	Slightly subdued	Disabling not	Emergency room visit or
(increased sleep)	prolonged	interfering with	interested in usual	hospitalization for severe
-	sleeping bouts	daily activity	daily activity	drowsiness (increased sleep)
Irritability	Easily consolable	Requiring	Inconsolable;	Emergency room visit or
(fussiness)		increased	crying cannot be	hospitalization for severe
		attention	comforted	irritability (fussiness)
(synonymous with				
restless sleep;				
decreased sleep)				

Abbreviation: CRF = case report form.

Maximum temperature range over the period from Day 1 through Day 7 will be mapped into the ranges described in Table 4 for summary of maximum temperature. Fever will be grouped into ranges for the analysis according to Table 4.

Table 4. Ranges for Fever

≥38.0°C to 38.4°C	
>38.4°C to 38.9°C	
>38.9°C to 40.0°C	
>40.0°C	

Note: Fever is defined as temperature ≥ 38.0 °C.

a. Grade 4 assessment should be made by the investigator. Grade 4 will not be collected in the e-diary but will be collected as an AE on the CRF.

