6.1.1.1.1. Main Analysis

- Estimand: Proportions of participants reporting prompted local reactions (redness, swelling, and pain at the injection site) within 7 days after the last assigned vaccination.
- Analysis set: Safety population (Section 4).
- Analysis time point: Within 7 days after the last assigned vaccination.
- Analysis methodology: Descriptive statistics.
- Reporting results: Proportions of participants reporting prompted local reactions will be summarized by maximum severity level. The percentage (%), the numerator (n), and the denominator (N) used in the percentage calculation, and the corresponding 95% Clopper-Pearson CI will be presented for each vaccination group.

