6.1.1.2. Systemic Events

6.1.1.2.1. Main Analysis

- Estimand: Proportions of participants reporting prompted systemic events (fever, decreased appetite, irritability, and drowsiness/increased sleep) within 7 days after the last assigned vaccination.
- Analysis set: Safety population (Section 4).
- Analysis time point: Within 7 days after the last assigned vaccination.
- Analysis methodology: Descriptive statistics.
- Reporting results: The percentage (%), the numerator (n), and the denominator (N) used in the percentage calculation, and the corresponding 95% Clopper-Pearson CI will be presented for each vaccination group.

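### Maximum severity of prompted reactions comes from e-diary grades only, so by-severity summaries stop at Grade 3 and no visible output shows an investigator-classified Grade 4 as such

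*SAP*

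**What the plan says.** SAP Table 2 defines four grades for redness, swelling and pain, and SAP Table 3 defines four for decreased appetite, drowsiness and irritability. Fever is handled by temperature range (SAP Table 4) and has no Grade 4.

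- **Who assigns Grade 4.** Protocol 8.2.3.1: "Only an investigator is able to classify a participant's local reaction as Grade 4". Protocol 8.2.3.2.1 has the same rule for systemic events. Both require immediate notification of the sponsor.
- **Where it is recorded.** SAP 3.1.1.1: "Grade 4 will not be collected in the e-diary but as an AE on the CRF". SAP 3.1.1.2 says the same for systemic events. The footnotes to Protocol Tables 1 and 2 add that severity is then graded on the general AE scale, which is set out in Protocol 10.2.3.
- **How maximum severity is derived.** SAP 3.1.1.1 takes the highest grade "among severity grades reported for that local reaction in the e-diary". Redness and swelling are "categorized during analysis as mild, moderate, or severe based on the grading scale in Table 2". For systemic events, SAP 3.1.1.2 states: "The derivations for systemic events will be handled similarly to the way local reactions are handled for severity level".
- **What is tabulated.** SAP 6.1.1.1.1: "Proportions of participants reporting prompted local reactions will be summarized by maximum severity level". SAP 6.1.1.2.1 names no severity split for systemic events; it says only "Reporting results: The percentage (%), the numerator (n), and the denominator (N) used in the percentage calculation", with a confidence interval. Protocol 9.3.4 plans both sets of events "by maximum severity and cumulatively across severity levels".

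**The concern.** The severity scale has four grades, but the derivation reads from a source that holds only three. A child whom the investigator has classified as Grade 4 is shown at whatever grade the parent entered.

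This matters most for redness and swelling. Grades 1 to 3 there measure size, while Grade 4 is tissue damage, so the two need not move together and a necrotic reaction can sit in a mild or moderate row.

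Describing safety is a primary objective and no hypothesis is tested, so the descriptive tables are the result. A table that cannot show the top grade of its own scale also cannot document that no such event occurred.

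**Working it through.** **Step 1: the ceiling.** Redness and swelling are entered in caliper units from 1 to 15, where 15 stands for more than 14 (Protocol 8.2.3.1). SAP Table 2 maps 1-4 to Grade 1, 5-14 to Grade 2 and above 14 to Grade 3. Pain, appetite, drowsiness and irritability are entered as mild, moderate or severe. Over all permitted entries the highest derived grade is 3 for each of these six events. A Grade 4 row built by this rule would always read 0/N.

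**Step 2: where a Grade 4 case lands.**

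| Event | Grade 4 criterion (SAP Tables 2, 3) | Derived grade |
|---|---|---|
| Pain, appetite, drowsiness, irritability | Emergency room visit or hospitalization for a severe symptom | Usually 3, so the total at Grade 3 or above does not change |
| Redness | Necrosis or exfoliative dermatitis | Set by diameter: 1, 2 or 3 |
| Swelling | Necrosis | Set by diameter: 1, 2 or 3 |

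Example: 4 units x 0.5 cm = 2.0 cm, the upper end of Grade 1. With necrosis this is Grade 4 in Table 2 but is tabulated as Grade 1, so it is also missing from the total at Grade 3 or above.

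**Step 3: whether the AE outputs restore the grade.** SAP 6.1.1.3.1 tabulates AEs by system organ class and preferred term. SAP 3.1.1.4 adds summaries and listings of related, severe and immediate AEs, and SAP 6.1.1.4.1 covers SAEs. The CRF severity is on the scale in Protocol 10.2.3, where Grade 4 means life-threatening. That is not the Table 2/3 criterion, so neither the preferred term nor the AE grade identifies a prompted Grade 4.

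Timing adds a gap. For the 2-dose group, SAP 6.1.1.3.1 and 6.1.1.4.1 count from the last vaccination to 1 month after it. A Grade 4 event after Dose 1 in that group is outside both main analyses and may appear only in supporting summaries.

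**Step 4: size.** The documents give no Grade 4 rate, so the plan has no figure of its own to reproduce for this point. Take n = 120 per group (Protocol 9.5). Clopper-Pearson limits are BetaInv(0.025; x, n-x+1) and BetaInv(0.975; x+1, n-x).

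- x = 0: 0%; upper limit 1 - 0.025^(1/120) = 3.03%.
- x = 1: 1/120 = 0.83%; limits 0.02% and 4.56%.

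The chance of at least one case in a group is 1 - (1-p)^120. At assumed rates of 0.2%, 0.5%, 1% and 2% it is 21%, 45%, 70% and 91%. The last two agree with 70.1% and 91.1% in Protocol Table 5.

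**Step 5: no diary grade entered.** The diary accepts entries only in a fixed window (Protocol 8.2.2) and missing diary data are not imputed (Protocol 9.1.1). Let k other children have the reaction. The correct any-grade proportion is (k+1)/120.

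- Child stays in N: the proportion becomes k/120, a fall of 1/120 = 0.83 points.
- Child leaves N: it becomes k/119. At k = 0 the fall is again 0.83 points. At k = 59 it is 60/120 - 59/119 = 50.00% - 49.58% = 0.42 points.

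SAP 6.1.1.1.1 does not say which N applies.

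**The case against.** The strongest reply is that this is a disclosed design. The SAP states, in text and in table footnotes, that Grade 4 is not in the diary, and it gives the names mild, moderate and severe to Grades 1-3 only. A severity row therefore reports what the parent recorded and claims nothing more. That stands as far as it goes: no passages conflict, and keeping parent and investigator assessments apart is reasonable. What is missing is a link from the investigator's classification back to the prompted-event tables.

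Second, the event is captured. It is an AE, the sponsor is notified at once, inpatient hospitalization is an SAE criterion (Protocol 10.2.2), and rare cases can be read in listings. A reader might infer that Grade 4 events vanish from safety reporting. The documents do not support that. The gap is one of classification and display, apart from the 2-dose group after Dose 1, where the main AE and SAE windows do not reach.

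A reader might also infer that the primary estimands are biased. They are any-event percentages, so with a completed diary they do not change. Staff review of diaries, ideally daily (Protocol 8.2.2), should keep missing entries uncommon.

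Third, a Grade 4 row cannot be built from the AE severity field, because that field uses the other scale, and no visible text shows a dedicated CRF field. This stands, and the data source has to be named.

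Finally, some SAP text is not supplied. There may be a Grade 4 listing that cannot be seen, so the claim is limited to visible outputs.

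**Conclusion.** The point holds as a reporting gap that should be closed; it does not threaten the primary results. Under the stated rule, by-maximum-severity summaries of local reactions (SAP 6.1.1.1.1) and of the three systemic symptoms (planned in Protocol 9.3.4) cannot exceed Grade 3. The substantive error is confined to necrosis or exfoliative dermatitis with a small measured area, which can be shown as low as Grade 1.

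Few cases are expected: each one is 0.8% of a group of 120, and an explicit zero would carry an upper 95% limit of 3.0%. The 0.8-point loss from the any-grade percentage when no diary grade exists assumes that the child stays in the denominator; otherwise it is smaller once the reaction is common, about 0.4 points at 50% incidence. Confidence is high on the derivation rule and lower on the absence of any Grade 4 output, because the supplied SAP is incomplete.

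**What to change.** Keep the e-diary derivation in SAP 3.1.1.1 and 3.1.1.2 and label its rows as e-diary Grades 1-3. For every prompted event except fever, add a separate row, or at minimum a footnoted count, by group and dose. It should give the participants with an investigator-classified Grade 4 under SAP Table 2 or 3 and onset on Day 1-7. Place it with the local reaction summary in 6.1.1.1.1 and with the systemic severity summary that Protocol 9.3.4 plans, which 6.1.1.2.1 should then name.

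State the source: a CRF field if one exists; otherwise the Grade 4 sponsor notifications, reconciled to the AE records before database lock. Do not use the general AE severity grade. Footnote the row as investigator-reported and also recorded as an AE. Reporting by dose makes a Dose 1 event in the 2-dose group visible.

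The cost is a label, a row and a footnote, plus a small case-level reconciliation if there is no CRF field. The event will appear in two places, which the footnote explains. No new assessment is needed, since the investigator already classifies the event, records it as an AE and notifies the sponsor.
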